2. Secondary obesity or diabetes.
3. Serious systematic diseases, such as digestive diseases, tumor, cardiac, pulmonary, renal, rheumatic and immune system diseases.
4. Pregnant women, women ready for pregnancy, and nursing mothers.
5. Take antibiotics or bacterial agents within 1 month
6. Diarrhea or abscess in 1 month or blood or other abnormal feces
7. Diabetics history more than 2 years
8. The OGTT experiment $FG \geq 9 \text{ mmol/L}$ or $2h \geq 14 \text{ mmol/L}$ in diabetic patients

Study settings

The interventions and laboratory tests and performed and managed at the Health Care Center, Southwest Hospital, Chongqing, and Health management institute, PLA General hospital, Beijing, China.

Trial design

Interventions

1. Probiotics group: Diabetes/prediabetes participants take four packs of probiotics a day on an empty stomach with 200ml water every morning. The probiotics is called KAWAI, each pack contains 880 billion dead *Lactobacillales* (*S. thermophilus*) .
2. Placebo group:
Diabetes/prediabetes participants take four packs of probiotics a day on an empty stomach with 200ml water every morning.

Primary and secondary outcomes

Primary outcomes:

1. Blood glucose levels(FBG and OGTT), insulin sensitivity(Insulin, C-peptide)
2. Gut microbiota composition

Secondary outcomes:

1. Blood inflammatory markers
2. Diabetes risk factors (blood pressure, blood lipids)
3. Weight, waist circumference, BMI, Body composition
4. Intestinal endocrine function (GPL-1)
5. Gut microbiota metabolites

The primary and secondary outcome measures will be assessed at baseline, 1- and 3-month time points.

Measurements procedures

1. Screening:

The potential subjects will be selected from the outpatient pool of those who have records of abnormal blood glucose level in 2017. Registered nurses from health care center will first contact the potential subjects and invite them to a

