after the intake of 75 g glucose for the assessment of serum insulin, and glucose. Venous blood samples will be taken in standardized fasting conditions at 7–8 a.m. Total cholesterol, high-density lipoprotein (HDL), low-density lipoprotein (LDL), triglycerides, will be measured from serum sample by conventional methods. ELISA can be used to assess serum samples for adiponectin, tumor necrosis factor alpha (TNF α), C-reactive protein (CRP), interleukin (IL-6), interleukin 10 (IL-10), and lipopolysaccharides (LPS). Gut microbiota metabolites will be measured from serum sample by LC-MS/MS.

3. Fecal samples collection

The fecal samples (two samples per each time) will be collected in the health care center during the second day of the 3-day dietary records collection. The study will provide to subjects the materials for sample collection. The subjects are advised to sample approximately 2–3 grams of feces by spatula attached to the cover of the plastic specimen jar. Fecal samples are frozen after collection within 30 min, stored at -80°C . 16SrDNA sequencing will be performed. Different bacterial indices will be calculated to evaluate the interrelationship of different bacterial species and how they are associated with diabetes.

4. Body composition

Bioelectrical impedance analysis will be used to estimate lean tissue mass (LM), fat mass (FM) and bone mass (BM) of the whole body, legs, arms, and trunk as well as android and gynoid regions.

Concomitant adherences and procedures

To ensure good compliance in probiotics and placebo group, we will keep in contact with them via phone call monthly questionnaire to check on their physical condition and lifestyle at 1 and 3months follow-up during the intervention.

Sample size estimation

The sample size calculation with an estimate of how many participants will be needed for the primary outcome to be statistically, clinically and/or politically significant. For the specific primary outcome of blood glucose and microbiota, based on our pilot study, 68 prediabetes subjects in each group would have 85% power for mean comparison between the randomized groups for the fast

blood glucose. We set the significance level at 0.05 and allowed for 10 mean comparisons with the Bonferroni correction between the groups. Taking into account the compliance and drop-out (15%), we increase our sample size to 80 in each prediabetes group. With the same approach, sample size for each diabetes group is 60 subjects.

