Randomization methods

1. Randomization Process:

SPSS will be used for generating the randomization assignment for Diabetes groups and prediabetes groups respectively. Randomization numbers will be generated and sealed in an envelope and kept by the study coordinator. On the basis of subjects' enrolment time when 20 qualified subjects are reached, the study coordinator will open one block to allocate subjects into each group.

2. Blinding:

Both subjects and investigators will be blinded with respect to the randomization assignment of each participant. The investigators will remain blinded until the completion of the study. The study coordinator will be blinded from which group the participants are signed in. The accuracy of the randomization log is the responsibility of the study coordinator.

Statistical methods

All data collected by questionnaires will be entered into database management software (EpiData), double checked by independent researchers, and exported to SPSS statistics version. If data is not normally distributed, their natural logarithms will be used for further analysis.

Descriptive statistics will be used to present the background and anthropometric data at the baseline and follow-up assessments as mean and 95% confidence interval (CI) unless otherwise stated.

An intention-to-treat (ITT) analysis will be performed to compare the Probiotics group to Placebo group. The effects of the interventions will be assessed using analysis of variance (ANCOVA) for repeated measures (treatment group \times time) and baseline difference as a covariate. If the significance of the group by time interaction is $p < 0.05$, the effect will be localized utilizing Bonferroni for multiple comparisons. The level of statistical significance chosen for the contrasts will be $p < 0.05$. In addition to the ITT

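### Gut microbiota composition is a primary outcome with no defined measure, and the ten-comparison Bonferroni allowance used for sizing is not carried into the analysis, so familywise error is uncontrolled

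*Protocol*

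**What the plan says.** **Outcomes.** Under Primary and secondary outcomes, the Protocol gives two primary items. The first is "Blood glucose levels(FBG and OGTT), insulin sensitivity(Insulin, C-peptide"), which is at least four variables. The second is "Gut microbiota composition", with no index, taxonomic level or number of variables. On timing it says "The primary and secondary outcome measures will be assessed at baseline, 1- and 3-month time points", and names no time point as primary.

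**Measurement.** Under Fecal samples collection, "16SrDNA sequencing will be performed". The next sentence reads "Different bacterial indices will be calculated to evaluate the interrelationship of different bacterial species and how they are associated with diabetes". The indices are neither named nor counted, and the sentence describes association rather than a comparison of treatment groups.

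**Treatment-effect test.** Statistical methods in the Protocol, and Statistical plans in the SAP, use the same wording: "The effects of the interventions will be assessed using analysis of variance (ANCOVA) for repeated measures", in treatment group by time, without distinguishing one outcome from another. A group-by-time interaction below 0.05 leads to localisation with Bonferroni. "The level of statistical significance chosen for the contrasts will be" p < 0.05. A later analysis, an ANCOVA on percentage change, also uses Bonferroni. Correlation, regression and systems biology models are named for relationships and for integrating the microbiota data.

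**Sample size.** The Sample size estimation section, which names blood glucose and microbiota together, sets 0.05 with Bonferroni for ten comparisons of means. It arrives at 68 per prediabetes group for 85% power on fasting glucose, raised to 80 for 15% drop-out.

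**The concern.** Composition measured by 16S sequencing is a profile of many quantities. Calling it primary without saying which quantity decides the matter leaves the number of primary tests open. The efficacy rule then takes each variable separately and tests its interaction at 0.05 with no adjustment. The Bonferroni step that follows works among the contrasts of a variable that has already passed, so it does nothing for the number of variables that were tried.

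The sample-size section budgets for multiplicity and the analysis sections do not, so the trial is sized under one error rule and analysed under another. At stake is whether a positive microbiota result could be read as success on a primary outcome. As written, a significant index or genus could be reported that way without the reader knowing how many were examined.

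**Working it through.** **1. The plan's own figures.** Per-comparison level: 0.05 / 10 = 0.005. Drop-out step: 68 / (1 − 0.15) = 80, which reproduces. The 68 itself cannot be checked, because no difference or SD is given. Solved backwards at two-sided 0.005 and 85% power (sidedness is my assumption), the normal approximation gives d = (2.807 + 1.036) × √(2/68) = 0.659 SD.

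**2. Familywise error under the analysis rule.** For k independent tests at level α with no treatment effect, the chance of at least one false positive is 1 − (1 − α)^k. The documents give no k, so a range is shown. The last column applies the sample-size level instead.

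| k (assumed) | Each at 0.05 | Each at 0.005 |
|---|---|---|
| 5 | 23% | 2.5% |
| 10 | 40% | 4.9% |
| 20 | 64% | 9.5% |
| 50 | 92% | 22% |
| 100 | 99.4% | 39% |

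For example, 1 − 0.95^10 = 0.401 and 1 − 0.995^10 = 0.049.

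The row k = 5 needs no taxon-level testing. The four metabolic primaries plus a single microbiota index already make five. Done in both the diabetes and the prediabetes population, that is ten.

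**3. Effect of correlation.** Taxa and indices are not independent. Simulating equally correlated normal test statistics (20,000 runs) at two-sided 0.05 gives:

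| k | Correlation 0.3 | Correlation 0.5 |
|---|---|---|
| 10 | 35% | 29% |
| 50 | 81% | 62% |
| 100 | 94% | 78% |

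Correlation lowers the risk but does not bring it near 5%.

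**4. When a false positive becomes near-certain.** A 95% chance needs k ≥ ln(0.05) / ln(0.95) = 58.4, so 59 independent tests at 0.05. At 0.005 it needs ln(0.05) / ln(0.995) = 597.6, so 598.

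**5. What a longer primary list would cost.** Taking 0.659 SD as an example and testing each of k comparisons at 0.05/k, power at 68 per group is 85% for k = 10, 79% for k = 20, 71% for k = 50 and 64% for k = 100. A short list keeps the power the trial was sized for.

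**The case against.** The strongest reply is that the sponsor did consider multiplicity. The ten-comparison allowance sits in a paragraph that names microbiota, and ten indices each tested at 0.005 would have a familywise error of 4.9%. That stands as evidence of intent. It is not an analysis rule: the ten are not identified, and both analysis sections state 0.05 without it. Nor would it cover a taxon list, since 50 taxa at 0.005 still give 22% if independent.

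Several stronger readings are tempting, and the documents do not support them:

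- **That false positive primary results are almost certain.** This needs about 59 or more independent tests at 0.05. Neither document says that each taxon will be tested as a primary result; the Protocol speaks of indices. With 5 to 10 of these the risk is 23% to 40%.
- **That repeated-measures ANCOVA is the only analysis, with Bonferroni confined to its follow-up contrasts.** The percentage-change ANCOVA also uses Bonferroni, and systems biology models are named for the microbiota data. None of these defines a family across outcomes or taxa, so the gap remains.
- **That chance findings will be fed into the mediation analysis.** Objective 3 names mediation, but neither document states a mediation model or a rule for choosing taxa by significance. The risk is left open, not planned.

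It is also fair to say that the percentages count a significant interaction. Claiming a localised effect additionally requires an adjusted contrast, so the rate per variable for that claim is at most 5%.

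**Conclusion.** The concern holds in a limited form. Microbiota composition is a co-primary outcome with no deciding measure or test. The treatment comparison uses an unadjusted 0.05 for each variable. The correction assumed when the trial was sized is missing from the analysis. This is more than missing detail, because the stated rule applied even to a handful of primary variables exceeds 5%: about 23% for 5 independent tests and 40% for 10.

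The larger figures, 92% for 50 taxa and 99% for 100, are conditional. They assume taxon-by-taxon testing at 0.05 and independence, and fall to 62% and 78% at correlation 0.5. All the figures rest on an assumed number of tests and, where populations are not combined, refer to one population.

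**What to change.** In the SAP:

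1. Name one primary microbiota test in each population at one time point. One option is a PERMANOVA of treatment on month-3 community distances, adjusted for baseline. A single prespecified diversity index would also serve.
2. List the primary comparisons, ten at most, and test each at 0.005 as the sample size assumed. Say whether the ten span both populations. Four metabolic variables plus one microbiota test, in two populations, makes 2 × 5 = 10 if each is counted once at one time point; the documents do not say that this was intended. Ten in each population would give 1 − 0.995^20 = 9.5% over the whole trial.
3. Make single taxa and all other indices secondary or exploratory, with Benjamini-Hochberg control at 5% across those tested, and report the number tested.

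This is wording and standard software, with no added participants, samples or visits. The downside is that fewer individual taxa will be declared significant, and month-1 microbiota results become supportive if month 3 is chosen.

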STUDY PROTOCOL

Effect of probiotics on T2DM and pre-diabetes in China ---the role of gut microbiota composition

Background

According to recent surveyed, diabetes prevalence rate in Chinese adults had gone up to 11.6%, the pre-diabetics diabetes prevalence rate was 50.1%. Effective intervention is urgently needed. Study of relationship between intestinal flora and diabetes is a hot topic at present. Gut microbiota disorders may be involved in the development of diabetes by means of increasing the number of inflammatory mediators, chronic inflammation, insulin resistance, increased energy intake, and obesity ect. In view of the correlation between gut microbiota and diabetes, gut microbiota can be taken as an important target for diabetes intervention. In this study, we aim to explore whether probiotics intervention affect blood glucose level and Risk factors for diabetes in T2DM and pre-diabetes via modification of gut microbiota composition and other post-interventional effects.

Objectives :

1. To investigate the effects of probiotics intervention on blood glucose metabolism (blood glucose, insulin sensitivity) and diabetes risk factors (blood lipid, weight, body composition, inflammatory state) in diabetes and pre-diabetes.
2. To investigate the effect of probiotics intervention on gut microbiota composition and its correlated metabolite.
3. To investigate the mediating effect of gut microbiota on glucose control in diabetes and pre-diabetes.

Methods/design

Trial design

This is a four-arm randomized controlled trial (Diabetes-intervention n=30, Diabetes-control n=30, prediabetes-intervention n=80, prediabetes-control n=80) . Participants are recruited from the outpatient registration pool of those who have participated in annual health checks for diabetes during 2017 to 2018 at Health care Center, Southwest Hospital, Chongqing, China. After an initial screening, potential subjects will be assessed for inclusion in the run-in trial. Those subjects who meet the inclusion criteria will be then invited to the intervention study for a total duration of 3 month. Those participants who are qualified for the intervention study will be randomized into intervention or control group after baseline assessments.

Eligibility criteria

Inclusion criteria:

1. The patient was diagnosed with pre-diabetes or diabetes by OGTT
2. Age: 18-60y
3. BMI:18-35kg/m²

Exclusion criteria:

1. Patients who have diabetes, hyperlipemia , and need regular use of drugs.

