study information meeting. Detailed information of the objectives of the study, its nature and constraints, the anticipated risks and the expected benefits are given by the investigating physician of endocrinology and professor of sport medicine in the recruitment information meetings. When the screening consent form has been signed, patients will be asked to fill in a screening questionnaire to check their health and medication background as well as alcohol consumption, and to undergo a glucose tolerance test (blood draw after overnight fasting, followed by samples of 2 hours after the intake of 75 g of glucose).

Follow-up visits

The purpose of the follow-up visits is to monitor the compliance, enhance retention of the subject in the study, and obtain information on factors that may affect outcomes of the study. A study coordinator will contact participants every month to check their oral probiotics records. The study coordinator will also give feedback. The participants will have follow-up visits to the laboratory of Health care Center, Southwest Hospital, Chongqing at months 1, 3. Their height, weight, blood pressure, blood samples, fecal samples, and changes in health status and body composition will be checked at those time points.

Methods of measurements

1. Questionnaire, anthropometry and physical examinations

Background information regarding lifestyle, behavioral and motivational characteristics as well as medical history will be collected by questionnaires. Data gathered from eligible subjects will then be used to describe the study populations, and individual results will be used to screen the changes and for monthly feedback.

Height will be determined using a wall-fixed measuring device, and weight using a calibrated scale. Height and weight will also be used to determine body mass index (BMI, weight(kg)/(height(m))²). Blood pressure will be measured after 5 min rest. A physician will examine the physical conditions of subjects and ensure that subjects meet the inclusion criteria.

2. Blood samples

Glucose tolerance tests will be performed after overnight fasting and 2 hours

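### If the baseline OGTT is a separate test from the screening OGTT, the screening glucose is an unused pre-randomisation covariate; the plan should say which it is and, if separate, adjust for both values

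*Protocol*

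**What the plan says.** - **Entry.** Inclusion criterion 1 reads "The patient was diagnosed with pre-diabetes or diabetes by OGTT", so every participant has a qualifying OGTT. The screening section describes it: patients "undergo a glucose tolerance test (blood draw after overnight fasting, followed by samples of 2 hours after the intake of 75 g of glucose". Exclusion criterion 8 sets upper limits on fasting and 2-hour glucose for diabetic patients.
- **Order.** Protocol, Trial design: "After an initial screening, potential subjects will be assessed for inclusion in the run-in trial". Those who qualify "will be randomized into intervention or control group after baseline assessments".
- **Outcomes.** The first primary outcome begins "Blood glucose levels(FBG and OGTT", and "The primary and secondary outcome measures will be assessed at baseline, 1- and 3-month time points". Screening is not listed as an outcome time point.
- **Models.** The repeated-measures ANCOVA (Protocol, Statistical methods; SAP, Statistical plans) has treatment group by time "and baseline difference as a covariate". The percentage-change ANCOVA controls for the baseline value. Neither names the screening value.
- **Sizing.** Sample size estimation is based on fasting glucose: 68 per prediabetes group for 85% power, raised to 80 for 15% drop-out.

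**The concern.** A single glucose reading is a noisy measure of a person's level. If a second reading taken before allocation exists, leaving it out of the model leaves explainable variation in the error term. Fasting glucose is the outcome on which the trial is sized, so its standard error is the one to reduce where existing data allow. At stake is a modest amount of precision on the two glucose measures. The ITT comparison is unbiased with or without the extra covariate.

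**Working it through.** **1. The plan's own figure.** 68 / 0.85 = 80.0, so the 80 per prediabetes group reproduces. The 68 cannot be checked, because the pilot difference and SD are not given.

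**2. Are there two readings?** For: screening and baseline are separate steps with a run-in assessment between them, and a randomisation block is opened only once 20 qualified subjects have accumulated, so many participants wait. Against: the only pre-randomisation OGTT actually described is the screening one, and the blood-sample section gives no time points. Two readings is the natural inference, but it is not stated.

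**3. Gain without selection.** Assume unit variance and equal correlation r between any two readings. The documents give no r. The residual variance of the month-3 value is 1 − r² with one pre-value and 1 − 2r²/(1 + r) with two.

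| r | one value | two values | reduction |
|---|---|---|---|
| 0.5 | 0.750 | 0.667 | 11.1% |
| 0.6 | 0.640 | 0.550 | 14.1% |
| 0.7 | 0.510 | 0.424 | 17.0% |

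The 0–3 month change adjusted for baseline has the same residual as the month-3 value adjusted for baseline, so it gains equally. In simulation the percentage-change ANCOVA gains almost as much (10.9%, 14.0% and 16.8%).

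**4. Gain with selection.** Entry depends on the screening OGTT, which narrows its range. Simulated normal data (2,000,000 draws), with entry limited on the standardised screening value:

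| entry window | r = 0.5 | r = 0.7 |
|---|---|---|
| above average only | 5.1% | 9.7% |
| 0 to 1 SD | 1.3% | 3.0% |
| 0.5 to 1.5 SD | 1.2% | 2.7% |

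The range is therefore about 1–10%. If one-baseline ANCOVA needed 68 per group, the same precision would need 68 × 0.988 = 67.2 to 68 × 0.903 = 61.4, before the cost in step 6.

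**5. The group by time test.** If time means months 1 and 3 only, the contrast is the month-3 minus the month-1 value. Its covariance with any pre-randomisation value is r − r = 0, so the gain is exactly zero. If baseline is a level of time, the 0–3 month change gains as in steps 3 and 4.

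**6. Cost of one covariate.** With N analysed in a stratum, going from one covariate to two inflates the variance by about (N − 4)/(N − 5).
- Prediabetes, N = 2 × 68 = 136: 132/131, or 0.8%.
- Diabetes at 30 per arm, N = 60: 56/55, or 1.8%. After 15% drop-out, N = 51: 47/46, or 2.2%.

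Net in diabetes at N = 51: a 1.3% cut gives 0.987 × 1.022 = 1.009, a small loss; a 9.7% cut gives 0.903 × 1.022 = 0.923.

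**7. Using the mean of the two values as one covariate.** With both values in the model each has coefficient r/(1 + r). The weights are equal, so for the month-3 value the mean loses nothing and costs no extra degree of freedom. This does not carry over when the response is a change from the single baseline value. The residual variance of that change given only the mean is 2(1 − r) − (1 − r)²/[2(1 + r)]. At r = 0.5 this is 1 − 0.083 = 0.917, worse than the 0.750 from baseline alone.

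**The case against.** The strongest objection is that the premise is not documented: no section says the OGTT is repeated at baseline, and if the screening test is the baseline test, the model already uses it. That stands, and it makes the point conditional. The plan also already adjusts for baseline, so omitting a second, range-restricted value is neither an error nor a bias. That stands too.

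The planned gate is the group by time interaction, which gains nothing if time means months 1 and 3. This is correct under equal correlation, but the percentage-change comparison and the adjusted difference at a visit do gain, so a benefit remains.

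A reader might infer more than the documents support:
- **That the gain is largest in the small diabetes groups.** The caps in exclusion criterion 8 narrow the screening range there, and a covariate costs about 2% of variance, which can cancel a small gain.
- **That the precision is free.** It needs no new data, but it does use a degree of freedom.
- **That pre-randomisation covariates keep every analysis unbiased.** The efficacy analysis depends on at least 60% compliance, which arises after randomisation. The reassurance covers the ITT comparison only.
- **That both glucose measures underlie the sample size.** Only fasting glucose does.

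**Conclusion.** The point holds as an optional and conditional efficiency gain. The order of steps implies two pre-randomisation readings of fasting and 2-hour glucose, and the models use only the baseline one. If the readings are separate, and the correlation is equal at 0.5–0.7, adjusting for both lowers the residual variance of the month-3 or 0–3 month group difference by about 1–10% after selection, with 11–17% as the figure without selection. The actual entry window, the correlation and the interval between the tests are not in the documents, so a narrower range cannot be defended. The net benefit is probable but small in prediabetes and uncertain in diabetes.

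The diabetes figures use the 30 per arm in Trial design. Sample size estimation gives 60 per diabetes group; the two must be reconciled separately.

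**What to change.** 1. In the Protocol (Measurements procedures), state whether the baseline OGTT is a separate test from the screening OGTT or the same one. If it is the same, nothing further is needed.
2. If separate, add to Statistical methods and to the SAP: for fasting and 2-hour glucose, the ITT repeated-measures and percentage-change models include the participant's screening value and baseline value of that measure as covariates.
3. Where a degree of freedom matters, as in the diabetes stratum, the mean of the two values may serve as a single covariate when the response is the follow-up value itself. For percentage change, or if baseline is a level of time, keep the baseline value in the model, or use the mean as the baseline throughout.
4. Make no claim that this adjustment protects the compliance-based efficacy analysis from bias.

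Cost: one clarifying sentence, one sentence in the analysis plan, and at most one degree of freedom per model. No new visits or samples are needed. The choice should be fixed before unblinding.

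### The sample size allows for ten Bonferroni-corrected comparisons that are never listed, and the analysis text states no error control across the primary measures.

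*Protocol*

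**What the plan says.** - **Protocol, Sample size estimation.** The calculation is introduced with "For the specific primary outcome of blood glucose and microbiota, based on our pilot study". It then states that "68 prediabetes subjects in each group would have 85% power for mean comparison between the randomized groups for the fast" blood glucose measure, at a significance level of 0.05, and that it "allowed for 10 mean comparisons with the Bonferroni correction between the groups". A 15% allowance for compliance and drop-out raises 68 to 80 per prediabetes group. No mean difference or SD is given.
- **Protocol, Primary and secondary outcomes.** The primary outcomes are "Blood glucose levels(FBG and OGTT), insulin sensitivity(Insulin, C-peptide") and "Gut microbiota composition". None is ranked first. On timing: "The primary and secondary outcome measures will be assessed at baseline, 1- and 3-month time points".
- **Protocol, Blood samples.** Insulin and glucose are taken fasting and at 2 hours.
- **Protocol, Randomization methods.** "SPSS will be used for generating the randomization assignment for Diabetes groups and prediabetes groups respectively". Each population is therefore its own two-arm comparison.
- **Protocol, Statistical methods, and SAP, Statistical plans (same wording).** The ITT analysis is a repeated-measures ANCOVA. The group-by-time interaction is tested at p < 0.05. If it is significant, Bonferroni is used to localise the effect, and contrasts are judged at p < 0.05. A percentage-change ANCOVA also uses Bonferroni, with an overall group difference at p < 0.05. A 95% CI that excludes zero counts as significance. The number of comparisons is not given for either use of Bonferroni.

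**The concern.** The sample size section shows that the sponsor meant to control error over a set of ten comparisons. The decision rules in the analysis text neither name that set nor use its level. Two analysts could follow different sections and disagree: a fasting glucose difference with unadjusted p = 0.02 meets a 0.05 threshold but not 0.05/10.

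Three things are at stake:

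- With five or more measures labelled primary and each tested at 0.05, the chance of at least one false primary claim within a population can be well above 5%.
- With the ten unlisted, the family could be settled after the results are seen.
- The 85% power refers to a corrected mean comparison that the analysis text does not specify.

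**Working it through.** **Inputs.** From the Protocol: significance level 0.05, ten comparisons, 85% power, 68 per prediabetes group, 15% loss (Sample size estimation); 30 per diabetes arm (Trial design); five named primary measures. Assumptions: two-sided tests (sidedness is not stated), equal correlation between measures, and a simple two-group comparison for power.

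**1. The plan's own figures.** Drop-out: 68 / (1 − 0.15) = 80, as stated. Level per comparison: 0.05 / 10 = 0.005. The 68 itself cannot be reproduced without the pilot difference and SD, so I solved for the standardised difference d that it implies. The normal approximation is d = (z for α/2 + z for 85% power) × √(2/68):

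- At 0.005: (2.807 + 1.036) × 0.1715 = 0.659; noncentral t gives 0.669.
- At 0.05: (1.960 + 1.036) × 0.1715 = 0.514; noncentral t gives 0.518.

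The documents do not allow a check of which applies. The t-based values are used below.

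**2. Chance of at least one false claim, per population.** For k independent tests at level α this is 1 − (1 − α)^k. For five at 0.05: 1 − 0.95^5 = 0.226. For equicorrelated two-sided z-tests with critical value c it is 1 − ∫ φ(u) [Φ((c − √ρ u)/√(1−ρ)) − Φ((−c − √ρ u)/√(1−ρ))]^k du.

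| Tests | Level | ρ = 0 | 0.3 | 0.5 | 0.7 |
|---|---|---|---|---|---|
| 5 | 0.05 | 0.226 | 0.209 | 0.183 | 0.148 |
| 5 | 0.01 | 0.049 | 0.047 | 0.042 | 0.035 |
| 10 | 0.01 | 0.096 | 0.087 | 0.073 | 0.054 |
| 10 | 0.005 | 0.049 | 0.045 | 0.039 | 0.029 |

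The divisor must match the family. A level of 0.01 suits five comparisons, but with ten it lets the error reach 9.6%.

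**3. Power for one two-group comparison (noncentral t).**

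| Setting | d | at 0.05 | at 0.005 |
|---|---|---|---|
| Prediabetes, 68 per group | 0.669 (sized at 0.005) | 97% | 85% |
| Prediabetes, 68 per group | 0.518 (sized at 0.05) | 85% | 57% |
| Diabetes, 30 per arm | 0.669 | 72% | 38% |
| Diabetes, 30 per arm | 0.518 | 50% | 19% |

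The diabetes rows assume the prediabetes effect size and no drop-out.

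**4. Interval width.** With 134 df the t multipliers are 1.978 (95%) and 2.854 (99.5%). Their ratio is 2.854 / 1.978 = 1.44.

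**The case against.** The strongest reply is that the analysis text does prescribe Bonferroni and never limits its scope. A contrast level of 0.05 is compatible with Bonferroni-adjusted p-values, and the ten may be exactly those contrasts. This stands as far as it goes. A reader might infer that the correction was dropped and that every primary measure is judged at an uncorrected 0.05; the documents do not support that, because neither set of comparisons is enumerated. But the reply does not reach the tests that come first. The interaction and the overall group difference are each at 0.05 for every measure, and nothing is said about control across measures.

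Other objections also stand in part:

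- The 23% to 15% range comes from five single tests, not from an interaction gate followed by contrasts. The upper end needs independence, which is unlikely for measures from the same blood draws. No rule says that success on any one measure is enough. The range is an illustration only.
- The plan says of the faecal samples: "Different bacterial indices will be calculated to evaluate the interrelationship of different bacterial species". A reader might take this as proof of many between-arm microbiota tests. The sentence concerns relations between species and with diabetes. It shows only that no single index is named.
- A reader might infer that 68 per group is wrong. Nothing shows that; it cannot be checked.

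**Conclusion.** The concern holds in this form: an allowance for ten comparisons is made at the design stage, the ten are undefined, the scope of Bonferroni in the analysis is unstated, and no control across the primary measures is stated on any reading. This is more than missing detail. Followed as written, the plan can raise the rate of false primary claims that its own sample size section set out to limit. The omission is certain from the text; the size of the inflation is not. The illustrative range rests on five tests, all nulls true and assumed correlations of 0 to 0.7. It would change if fasting and 2-hour values, visits or several microbiota indices were counted separately.

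**What to change.** Before unblinding, amend the Protocol's Sample size estimation and Statistical methods sections and the SAP:

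1. State one primary family for the ITT analysis within each population, so that error is controlled at 5% per population.
2. List its comparisons by measure (fasting or 2-hour value where both are taken), visit and named microbiota index.
3. Test each as a baseline-adjusted between-group difference from the repeated-measures model at 0.05 divided by the number listed. If there are ten, that is 0.005 with 99.5% CIs.
4. Say that for these comparisons this replaces both the 0.05 interaction gate and the within-model Bonferroni, so that the correction is neither bypassed nor applied twice.
5. Label the active-treatment and percentage-change analyses supportive.

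Alternatively, declare fasting glucose in prediabetes at one named visit the sole primary at 0.05 and label the rest secondary. Under either option, report the pilot difference and SD so that 68 can be checked.

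**Cost.** Wording only, with no added participants. Primary CIs become about 1.44 times as wide at 99.5%. For a simple fasting glucose comparison in prediabetes with 68 per group, 85% power is kept at 0.005 if 68 was sized there; if it was sized at 0.05, the power must be restated as about 57%. In diabetes with 30 per arm, power at 0.005 would be about 38% or 19%, against 72% or 50% at 0.05, so results there should be labelled accordingly. The Protocol gives 30 per diabetes group under Trial design and 60 under Sample size estimation; the two must be reconciled.
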